HUS describes TMA that affects mainly the kidney. It is characterized by MAHA, thrombocytopenia and acute renal failure. HUS includes various subtypes: verotoxin-associated typical (diarrheal) HUS, secondary HUS (of which, pregnancy-associated HUS is one type), and idiopathic atypical HUS (aHUS). Owing to similarity in clinical status & complications, diagnostic overlap with TTP can occur (**Fakhouri et al., 2012**).

Even in patients with congenital ADAMTS13 deficiency and recurrent acute episodes of TTP/HUS since infancy, pregnancy is one of the events that act as precipitating factors; occurring in approximately 5– 25% of

TTP cases (**Scully et al., 2008**). This is because pregnancy may provide multiple risk factors that can provoke an acute episode of TTP/HUS in a susceptible woman. These risk factors include increasing concentrations of procoagulant factors, decreasing fibrinolytic activity, loss of endothelial cell thrombomodulin, and decreasing activity of ADAMTS13 (**George, 2003**). These abnormalities become progressively more severe through the course of pregnancy, with the maximum abnormalities occurring at delivery and immediately postpartum. This is also the time of greatest risk for the occurrence of the more common pregnancy-related syndromes (pre-eclampsia, eclampsia, HELLP syndrome, and HUS). Differentiating these other syndromes from TTP may difficult or impossible because of similar clinical presentation in some aspects (**Stirling et al., 1984**). In many women, the distinction can only be determined by the course of illness following delivery (**McMinn and George, 2001**).

Reliable laboratory criteria specific for TTP are largely lacking. The diagnostic value of ADAMTS13 deficiency remains uncertain since not all TTP patients have severe deficiency (**Kremer Hovinga et al., 2010**), and not all documented severe ADAMTS13 deficiency patients meet TTP diagnostic criteria (**Scully et al., 2012**). Moreover, it is not feasible to constantly monitor ADAMTS13 activity

during therapeutic plasma exchange (TPE) in order to adjust therapy and monitor disease progress. Conjointly, relying on the therapeutic response to TPE harbors its own hazards and, besides, it has not been demonstrated that TPE is beneficial in treating non-idiopathic TTP. Thus, additional tests that could aid in the diagnosis and management of TTP are needed (**Sadler et al., 2008**).

Assessment of immature platelets was introduced as a non-invasive test of real time thrombopoiesis. They are newly released in the circulation with a larger size & greater RNA content than mature platelets, and can be measured by automated hematology analyzer equipped with reticulocyte detection channel and described as immature platelet fraction (IPF-%) and absolute immature platelet count (A-IPC). A high IPF-% has been suggested as an indicator of thrombocytopenia due to rapid platelet consumption, while a low IPF-% is characteristic of bone marrow suppression states. IPF-%/A-IPC has the competency to be performed routinely and, therefore, can provide therapeutic and diagnostic feedback in the compatible life threatening conditions (**Hong et al., 2013**).

Aim of work

The aim of this work is to show the utility of estimating IPF-% and A-IPC using a reticulocyte detection channel CBC auto analyzer as a simple reproducible blood analysis to be employed in the differential diagnosis of pregnancy-associated thrombotic microangiopathic conditions.

Patients and Methods

This study aiming to show the utility of estimating IPF-% and A-IPC using a reticulocyte detection channel CBC auto analyzer as a simple reproducible blood analysis to be employed in the differential diagnosis of pregnancy-associated thrombotic microangiopathic conditions. Patients were recruited from Ain Shams University Maternity Hospital.

Study sample was 57 women and were classified into three groups:

Group 1: *SPE/HELLP group.* This group will include 24 pregnant women (gestational age of >20 weeks) who are diagnosed as having TMA with provisional diagnosis of pre-eclampsia, HELLP syndrome.

Group 2: *TTP/HUS group.* This group will include 13 pregnant women (gestational age of >20 weeks) who are diagnosed as having TMA with provisional diagnosis of TTP/HUS.

Group 3: *Control group.* This group will include 20 pregnant women (gestational age of >20 weeks) having normal pregnancy with normal blood pressure and platelet count.

Inclusion criteria

Women will be included if they are:

- Older than 20 years of age
- Pregnant with singleton intrauterine pregnancy
- More than 20 weeks of gestation

Exclusion criteria

Patients will be excluded from the study if there was any of the following:

- Congenital malformation and fetuses with chromosomal or genetic syndrome.

- Recent blood transfusion.
- Refusal to participate in the study.
- BMI <18.
- Placental abnormalities like velamentous insertion.
- Multiple pregnancies.
- Known kidney disease.
- History of auto immune disease.

Ethical Considerations

An informed consent will be taken from each patient. The aim of the research was explained to patients. No harm was caused to patients as blood samples were routinely collected from patients.

Consent form:

Patient name:

Hospital number:

Information to the participant:

The procedure

- The results of your blood results and hospital data will be used in this clinical trial.
- An extra blood sample will be withdrawn at the time of diagnosis which is a simple procedure with no known complications.
- All your data and blood results, will saved confidentially and it will appear as a number in the results.
- The results of these investigation will not affect your management plan.

Methodology

An informed consent will be taken from each participant.

For all patients included in the study the following were done

1- Thorough history taking with special emphasis on:

- The gestational age will be estimated according to the last menstrual period and confirmed by a first trimesteric ultrasound.
- Past history to ensure the absence of any medical disorder included in exclusion criteria.

2- General, abdominal and local examination with particular emphasis on vital sign monitoring records.

Laboratory Investigations:

▪ **Haematological tests**

○ *Sampling:*

Five (5.0) ml of venous blood will be collected from each patient, it will be divided as follows:

- **Two (2.0) ml** added to an EDTA containing sterile tube for assessment of:
 - a) *Complete blood count (CBC)*, for estimation of hemoglobin concentration and platelet count using XE-2100® (Sysmex Corporation, Kobe, Japan) automated hematology system.
 - b) *Morphological assessment of different blood cells* with special emphasis on estimation of schistocyte counts (if present), achieved by microscopic examination of Romanowsky-stained PB smears prepared from an EDTA-anticoagulated PB sample. Schistocytes counting will be performed in at least 1000 RBCs in optimal areas of the film, with interpretation of results following the ICSH recommendations for identification, diagnostic value, and quantitation of schistocytes (**Zini et al., 2011**).
 - c) *Reticulocyte count*: by microscopic examination of supravitaly stained PB smear.

d) Estimation of IPF-% and A-IPC: All samples will be analyzed within 4 h of collection, using the XE-2100® (Sysmex Corporation, Kobe, Japan) automated hematology system. Using a carefully designed gating system in the XE-2100 optical (fluorescence) reticulocyte/platelet channel it is now possible to reliably quantify the IPF, employing upgraded software (XE-Pro Series; Sysmex). The flow cytometric IPF determination uses a proprietary fluorescent dye containing polymethine and oxazine. These two dyes penetrate the cell membrane, staining the RNA in the red cell and platelet reticulocytes. The stained cells are passed through a semiconductor diode laser beam and the resulting forward scatter light (cell volume) and fluorescence intensity (RNA content) measured. A computer algorithm discriminates the mature and IPF by the intensity of forward scattered light and fluorescence. The XE-2100 instrument used in the study was equipped with upgraded software for the data analysis of the IPF, which applies a preset gate to separate the two platelet populations. Mature platelets appear as blue dots and the immature platelets are displayed as green dots, the latter constituting the IPF parameter. Immature platelet fraction is usually expressed as a proportional value of the total optical platelet count to indicate the rate of platelet production, although an absolute count can also be obtained (**Briggs et al., 2004**).

- **Three (3.0) ml** are to be added to a sterile plain tube for serum assessment of: lactate dehydrogenase (LDH), serum bilirubin, liver enzymes (ALT & AST), serum uric acid, kidney function tests, using HITACHI 912 automatic analyzer (Roche Diagnostics GmbH. [name]).

Statistical methods:

Data will be analyzed using using IBM© SPSS© Statistics version 22 (IBM© Corp., Armonk, NY, USA) and MedCalc© version 14 (MedCalc© Software bvba, Ostend, Belgium).

The Shapiro-Wilk test to examine the normality of numerical data distribution. Normally distributed numerical variables will be presented as mean \pm SD and inter-group differences were compared using one-way analysis of variance (ANOVA) for multiple group comparison with application of the Schéffé test for post hoc pair-wise comparison, whenever the ANOVA test revealed a statistically significant difference among the groups.

Skewed numerical will be presented presented as median (interquartile range) and inter-group differences were compared non-parametrically using the Kruskal-Wallis test.

Categorical variables were presented as number (%) and differences will be compared using Fisher's exact test.

Correlations among numerical variables will be tested non-parametrically using the Spearman rank correlation.

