Figure (6): Box plot showing the immature platelet count (IPC) in patients with SPE/HELLP or TTP/HUS and normal controls. Box represents the range from the first to third quartile (interquartile range). Line inside the box represents the median (second quartile). Whiskers represent the range between the minimum and maximum values excluding outliers (rounded markers).

Assessment of Immature Platelet Fraction in Pregnancy-Associated Thrombotic Microangiopathy: (Results)

[figure not shown]

Figure (7): Box plot showing the immature platelet fraction (IPF) in patients with SPE/HELLP or TTP/HUS and normal controls. Box represents the range from the first to third quartile (interquartile range). Line inside the box represents the median (second quartile). Whiskers represent the range between the minimum and maximum values.

Assessment of Immature Platelet Fraction in Pregnancy-Associated Thrombotic Microangiopathy: (Results)

Table (6): Prevalence of a low platelet count, high IPF, or high schistocyte count among patients with SPE/HELLP or TTP/HUS and normal controls

Variable	SPE/HELLP (n=24)	TTP/HUS (n=13)	Control (n=20)	P-value¶
Low total platelet count (<100,000/mm ³)	9 (37.5%)	11 (84.6%)	0 (0.0%)	<0.001
High IPF (>11.2%) (Machin, 2010)	14 (58.3%)	10 (76.9%)	5 (25.0%)	0.008
High schistocyte count (>0%) (Gina et al.,2011)	14 (58.3%)	11 (84.6%)	0 (0.0%)	<0.001

Data are number (%).

¶Fisher's exact test.

[figure not shown]

Figure (8): Prevalence of a low platelet count, high IPF, or high schistocyte count among patients with SPE/HELLP or TTP/HUS and normal controls.

Table (7): Receiver-operating characteristic (ROC) curve analysis for discrimination between patients with TTP/HUS or SPE/HELLP using the IPF or schistocyte count

Marker

Assessment of Immature Platelet Fraction in Pregnancy-Associated Thrombotic Microangiopathy: (Results)

Index	IPF	Schistocyte count
Sample size	37	37
Positive group (TTP/HUS)	13 (35.1%)	13 (35.1%)
Negative group (SPE/HELLP)	24 (64.9%)	24 (64.9%)
Area under the ROC curve (AUC)	0.692 (0.519 to 0.833)	0.771 (0.603 to 0.893)
z statistic	2.028	3.022
P-value	0.043¶	0.003¶
Associated cut-off criterion	>15.9 %	>4.6 %
Sensitivity (%)	76.92 (46.2 - 95.0)	61.54 (31.6 - 86.1)
Specificity (%)	66.67 (44.7 – 84.4)	91.67 (73.0 – 99.0)
Positive predictive value (PPV, %)	55.6 (30.8 - 78.5)	80.0 (44.4 - 97.5)
Negative predictive value NPV, %)	84.2 (60.4 - 96.6)	81.5 (61.9 - 93.7)

Diagnostic indices are presented as value (95% CI).

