Figure (25): Comparison of ROC curves for discrimination between patients with TTP/HUS or SPE/HELLP using the IPF or schistocyte count.

Assessment of Immature Platelet Fraction in Pregnancy-Associated Thrombotic Microangiopathy: (Results)

Table (20): ROC curve analysis for discrimination between patients with TMA and normal controls using the IPF-%s or schistocyte count

Index	IPF-%	Schistocyte count
Positive group (TMA)	37 (64.9%)	37 (64.9%)
Negative group (normal controls)	20 (35.1%)	20 (35.1%)
Area under the ROC curve (AUC)	0.820 (0.695 to 0.909)	0.838 (0.716 to 0.922)
z statistic	5.678	8.660
P-value	<0.0001¶	<0.0001¶
Associated cut-off criterion	>8.1 %	>0 %
Sensitivity (%)	86.49 (71.2 - 95.5)	67.57 (50.2 - 82.0)
Specificity (%)	65.00 (40.8 - 84.6)	100.00 (83.2 - 100.0)
Positive predictive value (PPV, %)	82.1 (66.5 - 92.5)	100.0 (86.3 - 100.0)
Negative predictive value (NPV, %)	72.2 (46.5 - 90.3)	62.5 (43.7 - 78.9)

Diagnostic indices are presented as value (95% CI).

¶DeLong method.

- **(ROC) curve analysis for discrimination between patients with TMA or control using the IPF-%:** The optimal cutoff values for IPF-% for discrimination between patients with TMA or control was >8.1%. The sensitivity and specificity were 86.49% and 65%, respectively. The positive predictive value (PPV) and negative predictive value (NPV) were 82.1 % and 72.2%, respectively (**Table 20**), (**Figure 26**).

Assessment of Immature Platelet Fraction in Pregnancy-Associated Thrombotic Microangiopathy: (Results)

[figure not shown]

Figure (26): ROC curve for discrimination between patients with TMA and normal controls using the IPF.

- **(ROC) curve analysis for discrimination between patients with TMA or control using schistocyte count:** The optimal cutoff values for schistocyte count for discrimination between patients with TMA and normal controls was >0 %. The sensitivity and specificity were 67.57 % and 100%, respectively. The PPV and NPV were 100 % and 62.5%, respectively (**Table 20**), (**Figure 27**).

Assessment of Immature Platelet Fraction in Pregnancy-Associated Thrombotic Microangiopathy: (Results)

[figure not shown]

Figure (27): ROC curve for discrimination between patients with TMA and normal controls using the schistocyte count.

- **Comparison of the receiver-operating characteristic (ROC) curves:**

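### The >0 % schistocyte cut-off for TMA versus controls means one cell seen in an unstated number of cells, because the protocol sets only a minimum count

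*Protocol*

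**What the plan says.** The protocol (Laboratory Investigations, Haematological tests, item b) says "Schistocytes counting will be performed in at least 1000 RBCs in optimal areas of the film". For how the counts are to be interpreted, it defers to published ICSH guidance. It gives no fixed number, no maximum and no rule for when to read further. It does not say that the smear reader is masked to group.

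The SAP document, which holds completed results, states for TMA against controls: "The optimal cutoff values for schistocyte count for discrimination between patients with TMA and normal controls was >0" %. It continues: "The sensitivity and specificity were 67.57 % and 100%, respectively. The PPV and NPV were 100 % and 62.5%, respectively". The same figures stand in Tables 9 and 20, and Table 6 uses the same >0% threshold. No table or text in the results gives the number of red cells read per smear.

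Two pairs of tables disagree on the same material:

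- Control schistocyte count: 0.0 (0.0 to 0.0) in Table 4, but 0.01 (0.0 to 0.03) in Table 15.
- High-count threshold: >0% in Table 6, but >1% in Table 17, with the same 14 and 11 patients. The control cell of Table 17 is printed as 0.01 (0.0%) in a row of counts.

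**The concern.** When the measurement is a count, a cut-off of >0 % is a detection rule: a woman is positive if at least one schistocyte is seen. The chance of seeing one rises with the number of cells searched. With only a floor on that number and no report of what was done, sensitivity and specificity at this cut-off have no stated reference. Another laboratory that reads more cells applies a different test under the same name. An open-ended count also leaves room for smears from suspected cases to be searched longer than those from controls.

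The figures that depend on it are the schistocyte sensitivity, specificity, PPV and NPV in Tables 9 and 20, the Table 6 row, and the schistocyte AUC of 0.838 with which IPF-% is compared in Tables 10 and 21.

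**Working it through.** **1. Reproduce the reported figures.** From Table 6, positives are 14 of 24 SPE/HELLP, 11 of 13 TTP/HUS and 0 of 20 controls.

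- Sensitivity = (14 + 11)/37 = 67.57%, exact 95% CI 50.2 to 82.0.
- Specificity = 20/20 = 100%, CI 83.2 to 100.
- PPV = 25/25 = 100%; NPV = 20/(20 + 12) = 62.5%.
- With every control at exactly zero, AUC = (25 × 1 + 12 × 0.5)/37 = 0.838. The DeLong standard error is 0.0390, so z = 0.3378/0.0390 = 8.660.

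All match Tables 9 and 20. The ROC analysis therefore used zero for all 20 controls, and the whole schistocyte curve is one seen/not-seen call.

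**2. Dependence on cells read.** P(positive) = 1 − (1 − p)^n, where p is the true fraction and n the cells read. Both are assumed here; the documents give neither.

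| True fraction p | n = 1000 | n = 2000 | n = 5000 |
|---|---|---|---|
| 0.01% | 10% | 18% | 39% |
| 0.05% | 39% | 63% | 92% |
| 0.1% | 63% | 86% | 99% |
| 0.5% | 99.3% | >99.9% | >99.9% |

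The number of cells matters at very low fractions and hardly at all from 0.5% upwards. A reading of zero in 1000 cells is compatible with a true fraction of up to 1 − 0.05^(1/1000) = 0.30% (one-sided 95% bound).

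**3. How many of the 25 positives are low.** Table 4 gives an SPE/HELLP median of 0.5%. With 24 women, ranks 13 to 24 (12 women) are at or above 0.5%, which leaves 14 − 12 = 2 lower positives. The TTP/HUS lower quartile is 0.8%. With 13 women, ranks 4 to 13 (10 women) are at or above it, which leaves 11 − 10 = 1. So 22 of 25 positives read 0.5% or more, and about 3 may read less.

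**4. Effect of scoring only the first 1000 cells**, assuming the protocol minimum was met in every woman.

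- A woman with no schistocyte in all cells read has none in the first 1000. The 20 controls and 12 zero-read patients stay negative, so specificity and PPV stay at 100%.
- A positive woman may become negative. For a reading of 0.5% or more, the chance of none in the first 1000 is at most about 1 − 0.993 = 0.7%. Over 22 women that is an expected loss of at most 22 × 0.007 = 0.15.
- If all three low positives are lost, sensitivity = 22/37 = 59.5%, inside the reported interval. NPV = 20/35 = 57.1%. AUC = (22 + 15 × 0.5)/37 = 0.797, against 0.820 for IPF-%.

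**5. The conflicting tables.**

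- A single non-zero reading from 1000 cells is at least 0.1%. The median of 20 such readings (the mean of ranks 10 and 11) can be 0, 0.05%, 0.1% and so on, but not 0.01%.
- A control median above zero needs at least 10 of 20 controls above zero. Specificity at >0 % would then be at most 10/20 = 50%, not 100%.
- With an SPE/HELLP median of 0.5%, at most 12 of 24 can exceed 1%, so the 14 in Table 17 cannot belong to a >1% threshold.

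**The case against.** A minimum count is an ordinary precision floor. The protocol also defers to published recommendations that may fix the number. That source is not available here, and the citation is attached to interpretation, while the protocol's own counting rule remains a minimum.

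The stronger objection is that nothing in the documents shows counts differing between women or between groups. That stands. A reader might infer that cases were searched longer than controls, or that 67.57% and 100% are wrong. The documents support neither: the arithmetic is right, and the fault is a missing denominator.

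A reader might also take the true figures to be quite different. For example, if the zero-read patients had 0.02 to 0.1% and the controls 0.01 to 0.02%, reading 1000 further cells would give a sensitivity of about 73 to 88% and a specificity of about 82 to 90%. Those fractions are pure assumption. The figures also describe searching more cells, whereas fixing the count at 1000 cannot turn a zero reading positive.

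Finally, the point is peripheral to the aim. IPF-% and A-IPC are the tests under study, and schistocytes are the comparator. The differential comparison of TTP/HUS with SPE/HELLP uses >4.6 %, and the regressions use the schistocyte count as a percentage. All of this stands, and it is why the point is minor.

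**Conclusion.** The point holds as a minor, inexpensive improvement to definition and reporting. It is not a demonstrated error in the reported accuracy. At >0 %, sensitivity and specificity against controls are conditional on a number of cells that the plan leaves open and the results do not give. The women concerned are the 20 controls, the 12 patients read as zero and about 3 low positives; the other 22 positives would be called positive almost regardless.

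On a fixed 1000 cells, specificity would remain 100% and sensitivity would lie between 67.6% and, plausibly, about 59.5%. This rests on the medians and quartiles of Table 4, on at least 1000 cells having been read in every woman, and on the zero control readings behind Tables 6, 9 and 20. If the control values in Table 15 were the correct ones, that last assumption would fail. The finding of no significant AUC difference between the markers (0.018, −0.105 to 0.142, P = 0.7722) would very likely survive, though the paired data would be needed to confirm it.

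**What to change.** - **Protocol, item b:** replace the minimum with one fixed number of red cells for every woman, patients and controls alike (for example exactly 1000). Record numerator and denominator for each smear.
- **SAP, Tables 6, 9 and 20 and the accompanying text:** word the cut-off as at least 1 schistocyte per 1000 RBCs counted, in place of >0 %.
- **Recalculation:** where bench records identify the first 1000 cells, recompute Tables 6, 9, 10, 20 and 21 on them. Where they do not, report the denominators used, or that they are unknown, as a limitation on the 67.57% and 100% figures.
- **Reconcile:** the control values in Tables 4 and 15, and the threshold labels and control cell in Tables 6 and 17.

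The cost is a small wording change and, if the records allow, a short recalculation; no further blood is needed. Because the results are already complete, the wording change alone does nothing for existing data, and the documents do not say whether bench sheets record reading order. The downside is slightly less precision for any woman in whom more than 1000 cells were read. A fixed count makes the rule reproducible but does not make it more sensitive.

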Assessment of Immature Platelet Fraction in Pregnancy-Associated Thrombotic Microangiopathy: (Results)

**Assessment of Immature Platelet Fraction in Pregnancy-Associated Thrombotic
Microangiopathy: (Results)**

Assessment of Immature Platelet Fraction in Pregnancy-Associated Thrombotic Microangiopathy

Thesis

Submitted for Partial Fulfillment of Master Degree

in Clinical and Chemical Pathology

By

[name]

M.B, B.Ch.

Misr University for Science and Technology (MUST)

Under Supervision of

[name]. [name]

Professor of Clinical and Chemical Pathology

Faculty of Medicine- Ain-Shams University

[name] [name]

Lecturer of Clinical and Chemical Pathology

Faculty of Medicine- Ain-Shams University

[name] [name]

Lecturer of Obstetrics and Gynecology

Faculty of Medicine- Ain -Shams University

Assessment of Immature Platelet Fraction in Pregnancy-Associated Thrombotic Microangiopathy: (Results)

Results

Table (3): Characteristics of patients with SPE/HELLP or TTP/HUS and normal controls

Variable	SPE/HELLP (n=24)	TTP/HUS (n=13)	Control (n=20)	F/ χ^2	DF	p-value
Age (years)	29.5 ± 5.6	25.3 ± 4.5	26.0 ± 4.6	4.086	2, 54	0.022 ¶†
Parity				0.213	1	0.645§
P0	6 (25.0%)	2 (15.4%)	5 (25.0%)			
P1	5 (20.8%)	7 (53.8%)	5 (25.0%)			
P2	8 (33.3%)	2 (15.4%)	6 (30.0%)			
P3	2 (8.3%)	1 (7.7%)	3 (15.0%)			
P4	2 (8.3%)	1 (7.7%)	1 (5.0%)			
P5	1 (4.2%)	0 (0.0%)	0 (0.0%)			
Previous abortions				1.319	1	0.251§
Nil	23 (95.8%)	12 (92.3%)	18 (90.0%)			
One	1 (4.2%)	1 (7.7%)	1 (5.0%)			
Three	0 (0.0%)	0 (0.0%)	1 (5.0%)			
Gestational age (weeks)	30.5 ± 4.0 ‡	29.8 ± 5.4 ‡	24.2 ± 3.2	14.597	2, 54	<0.001 ¶

Data are mean ± SD or number (%).

¶One-way analysis of variance (ANOVA).

§Chi-squared test for trend.

†No statistically significant difference among the three groups by the Schéffé post-hoc test.

‡P-value <0.05 versus Control group (Schéffé test).

Assessment of Immature Platelet Fraction in Pregnancy-Associated Thrombotic Microangiopathy: (Results)

Table (4): Hemoglobin level, hematocrit, and schistocyte count in patients with SPE/HELLP or TTP/HUS and normal controls

Variable	SPE/HELLP (n=24)	TTP/HUS (n=13)	Control (n=20)	F	DF	P-value
Hemoglobin (g/dl)	10.5 ± 1.6	11.1 ± 1.9	11.4 ± 1.2	1.773	2, 54	0.180¶
Hematocrit (%)	32.3 ± 5.7	33.1 ± 6.5	34.9 ± 3.3	1.457	2, 54	0.242¶
Schistocyte count (%)	0.5 (0.0 – 1.2)†	6.5 (0.8 – 17.6)†‡	0.0 (0.0 – 0.0)	27.186	2	<0.0001§

Data are mean ± SD or median (interquartile range).

¶One-way analysis of variance (ANOVA).

§Kruskal-Wallis test.

†P-value <0.05 versus Control group (Conover test).

‡P-value <0.05 versus SPE/HELLP group (Conover test).

Assessment of Immature Platelet Fraction in Pregnancy-Associated Thrombotic Microangiopathy: (Results)

[figure not shown]

Figure (4): Box plot showing the total platelet count in patients with SPE/HELLP or TTP/HUS and normal controls. Box represents the range from the first to third quartile (interquartile range). Line inside the box represents the median (second quartile). Whiskers represent the range between the minimum and maximum values excluding outliers (rounded markers) and extreme observations (asterisks).

Assessment of Immature Platelet Fraction in Pregnancy-Associated Thrombotic Microangiopathy: (Results)

Table (5): Total platelet count, immature platelet count, and immature platelet fraction in patients with SPE/HELLP or TTP/HUS and normal controls

Variable	SPE/HELLP (n=24)	TTP/HUS (n=13)	Control (n=20)	χ^2	D F	P-value
Total platelet count (*1,000/mm ³)	121 (73 – 188.5)†	53.0 (37.0 – 81.0)†‡	269.5 (235.0 – 337.0)	35.333	2	<0.0001
Immature platelet count (*1,000/mm ³) A-IPC	14.875 (11.781 – 22.151)†	11.64 (6.410 – 21.238)†	21.992 (16.945 – 25.431)	10.362	2	0.006
Immature platelet fraction (%)IPF-%	13.0 (9.6 – 22.9)†	19.5 (15.1 – 27.7)†‡	7.2 (6.2 – 11.1)	18.897	2	<0.0001

Data are median (interquartile range).

†P-value <0.05 versus Control group (Conover test).

‡P-value <0.05 versus SPE/HELLP group (Conover test).

Assessment of Immature Platelet Fraction in Pregnancy-Associated Thrombotic Microangiopathy: (Results)

[figure not shown]

Figure (5): Box plot showing the total platelet count in patients with SPE/HELLP or TTP/HUS and normal controls. Box represents the range from the first to third quartile (interquartile range). Line inside the box represents the median (second quartile). Whiskers represent the range between the minimum and maximum values excluding outliers (rounded markers).

Assessment of Immature Platelet Fraction in Pregnancy-Associated Thrombotic Microangiopathy: (Results)

[figure not shown]

Figure (6): Box plot showing the immature platelet count (IPC) in patients with SPE/HELLP or TTP/HUS and normal controls. Box represents the range from the first to third quartile (interquartile range). Line inside the box represents the median (second quartile). Whiskers represent the range between the minimum and maximum values excluding outliers (rounded markers).

Assessment of Immature Platelet Fraction in Pregnancy-Associated Thrombotic Microangiopathy: (Results)

[figure not shown]

Figure (7): Box plot showing the immature platelet fraction (IPF) in patients with SPE/HELLP or TTP/HUS and normal controls. Box represents the range from the first to third quartile (interquartile range). Line inside the box represents the median (second quartile). Whiskers represent the range between the minimum and maximum values.

Assessment of Immature Platelet Fraction in Pregnancy-Associated Thrombotic Microangiopathy: (Results)

Table (6): Prevalence of a low platelet count, high IPF, or high schistocyte count among patients with SPE/HELLP or TTP/HUS and normal controls

Variable	SPE/HELLP (n=24)	TTP/HUS (n=13)	Control (n=20)	P-value¶
Low total platelet count (<100,000/mm ³)	9 (37.5%)	11 (84.6%)	0 (0.0%)	<0.001
High IPF (>11.2%) (Machin, 2010)	14 (58.3%)	10 (76.9%)	5 (25.0%)	0.008
High schistocyte count (>0%) (Gina et al.,2011)	14 (58.3%)	11 (84.6%)	0 (0.0%)	<0.001

Data are number (%).

¶Fisher's exact test.

[figure not shown]

Figure (8): Prevalence of a low platelet count, high IPF, or high schistocyte count among patients with SPE/HELLP or TTP/HUS and normal controls.

Table (7): Receiver-operating characteristic (ROC) curve analysis for discrimination between patients with TTP/HUS or SPE/HELLP using the IPF or schistocyte count

Marker

Assessment of Immature Platelet Fraction in Pregnancy-Associated Thrombotic Microangiopathy: (Results)

Index	IPF	Schistocyte count
Sample size	37	37
Positive group (TTP/HUS)	13 (35.1%)	13 (35.1%)
Negative group (SPE/HELLP)	24 (64.9%)	24 (64.9%)
Area under the ROC curve (AUC)	0.692 (0.519 to 0.833)	0.771 (0.603 to 0.893)
z statistic	2.028	3.022
P-value	0.043¶	0.003¶
Associated cut-off criterion	>15.9 %	>4.6 %
Sensitivity (%)	76.92 (46.2 - 95.0)	61.54 (31.6 - 86.1)
Specificity (%)	66.67 (44.7 – 84.4)	91.67 (73.0 – 99.0)
Positive predictive value (PPV, %)	55.6 (30.8 - 78.5)	80.0 (44.4 - 97.5)
Negative predictive value NPV, %)	84.2 (60.4 - 96.6)	81.5 (61.9 - 93.7)

Diagnostic indices are presented as value (95% CI).

¶DeLong method.

Assessment of Immature Platelet Fraction in Pregnancy-Associated Thrombotic Microangiopathy: (Results)

[figure not shown]

Figure (9): Receiver-operating characteristic (ROC) curve analysis for discrimination between patients with TTP/HUS or SPE/HELLP using the IPF.

Assessment of Immature Platelet Fraction in Pregnancy-Associated Thrombotic Microangiopathy: (Results)

[figure not shown]

Figure (10): Receiver-operating characteristic (ROC) curve analysis for discrimination between patients with TTP/HUS or SPE/HELLP using the schistocyte count.

Assessment of Immature Platelet Fraction in Pregnancy-Associated Thrombotic Microangiopathy: (Results)

Table (8): Comparison of the receiver-operating characteristic (ROC) curves for discrimination between patients with TTP/HUS or SPE/HELLP using the IPF-% or schistocyte count

Marker					
Index	IPF-%	Schistocyte count	Difference	z	P-value¶
Area under ROC (AUC)	0.692 (0.519 to 0.833)	0.771 (0.603 to 0.893)	0.079 (-0.171 to 0.328)	0.617	0.537

Diagnostic indices are presented as value (95% CI).

¶DeLong method.

[figure not shown]

Figure (11): Comparison of the receiver-operating characteristic (ROC) curves for discrimination between patients with TTP/HUS or SPE/HELLP using the IPF or schistocyte count.

Table (9): Receiver-operating characteristic (ROC) curve analysis for discrimination between patients with TMA and normal controls using the IPF-% or schistocyte count

Marker					
--------	--	--	--	--	--

Assessment of Immature Platelet Fraction in Pregnancy-Associated Thrombotic Microangiopathy: (Results)

Index	IPF	Schistocyte count
Sample size	57	57
Positive group (TMA)	37 (64.9%)	37 (64.9%)
Negative group (normal controls)	20 (35.1%)	20 (35.1%)
Area under the ROC curve (AUC)	0.820 (0.695 to 0.909)	0.838 (0.716 to 0.922)
z statistic	5.678	8.660
P-value	<0.0001¶	<0.0001¶
Associated cut-off criterion	>8.1 %	>0 %
Sensitivity (%)	86.49 (71.2 - 95.5)	67.57 (50.2 - 82.0)
Specificity (%)	65.00 (40.8 - 84.6)	100.00 (83.2 - 100.0)
Positive predictive value (PPV, %)	82.1 (66.5 - 92.5)	100.0 (86.3 - 100.0)
Negative predictive value (NPV, %)	72.2 (46.5 - 90.3)	62.5 (43.7 - 78.9)

Diagnostic indices are presented as value (95% CI).

¶DeLong method.

Assessment of Immature Platelet Fraction in Pregnancy-Associated Thrombotic Microangiopathy: (Results)

[figure not shown]

Figure (12): Receiver-operating characteristic (ROC) curve for discrimination between patients with TMA and normal controls using the IPF.

Assessment of Immature Platelet Fraction in Pregnancy-Associated Thrombotic Microangiopathy: (Results)

[figure not shown]

Figure (13): Receiver-operating characteristic (ROC) curve for discrimination between patients with TMA and normal controls using the schistocyte count.

Assessment of Immature Platelet Fraction in Pregnancy-Associated Thrombotic Microangiopathy: (Results)

Table (10): Comparison of the receiver-operating characteristic (ROC) curves for discrimination between patients with TMA and normal controls using the IPF or schistocyte count

Index	Marker		Difference	z	P-value¶
	IPF	Schistocyte count			
Area under ROC (AUC)	0.820 (0.695 to 0.909)	0.838 (0.716 to 0.922)	0.018 (-0.105 to 0.142)	0.290	0.7722

Diagnostic indices are presented as value (95% CI).

¶DeLong method.

Assessment of Immature Platelet Fraction in Pregnancy-Associated Thrombotic Microangiopathy: (Results)

[figure not shown]

Figure (14): Comparison of the receiver-operating characteristic (ROC) curves for discrimination between patients with TMA and normal controls using the IPF or schistocyte count.

Assessment of Immature Platelet Fraction in Pregnancy-Associated Thrombotic Microangiopathy: (Results)

Table (11): Multivariable binary logistic regression analysis for the relation between the IPF-% and TTP/HUS with adjustment for the confounding effect of the gestational age

Variable	Regression coefficient (B)	SE for B	Wald	P-value	Odds ratio (OR)	95% CI for OR
IPF -%	0.084	0.041	4.105	0.043	1.088	1.003 to 1.179
Gestational age (weeks)	-0.064	0.087	0.539	0.463	0.939	0.792 to 1.112
Constant	-0.271					

Table (12): Multivariable binary logistic regression analysis for the relation between the schistocyte count and TTP/HUS with adjustment for the confounding effect of the gestational age

Variable	Regression coefficient (B)	SE for B	Wald	P-value	Odds ratio (OR)	95% CI for OR
Scistocyte count (%)	0.101	0.052	3.781	0.052	1.107	0.999 to 1.226
Gestational age (weeks)	-0.052	0.088	0.355	0.551	0.949	0.799 to 1.127
Constant	0.420					

Table (13): Correlation between the IPF and schistocytes count in whole study population, patients with TMA, SPE/HELLP, or TTP/HUS, and normal controls

Correlation between IPF-% and schistocyte count			
Group	Number	Spearman rho (ρ)	P-value

Assessment of Immature Platelet Fraction in Pregnancy-Associated Thrombotic Microangiopathy: (Results)

All study population	57	0.466	0.0003
TMA	37	0.231	0.169
SPE/HELLP	24	0.190	0.375
TTP/HUS	13	-0.058	0.851
Control	20	0.000	-

[figure not shown]

Figure (15): Scatter plot showing the correlation between the IPF and schistocyte count in the whole study population. Fitted lines represent local regression smoothing (LOESS) trend lines.

Assessment of Immature Platelet Fraction in Pregnancy-Associated Thrombotic Microangiopathy: (Results)

[figure not shown]

Figure (16): Scatter plot showing the correlation between the IPF and schistocyte count in patients with TMA or normal controls. Fitted lines represent local regression smoothing (LOESS) trend lines.

[figure not shown]

Figure (17): Scatter plot showing the correlation between the IPF and schistocyte count in patients with SPE/HELLP or TTP/HUS and normal controls. Fitted lines represent local regression smoothing (LOESS) trend lines.

The results of the present study are shown in tables (14 -22) and figures (18-29).

✚ Comparison between patients with SPE/HELLP or TTP/HUS and normal controls regarding demographic features:

Assessment of Immature Platelet Fraction in Pregnancy-Associated Thrombotic Microangiopathy: (Results)

There was significant difference between the three studied groups regarding maternal age ($P < 0.05$) and high significant difference between the three groups regarding gestational age ($P < 0.001$). However, there was no significant difference between parity and previous abortions ($P > 0.05$). On applying Schéffé post-hoc test revealed no statistically significant difference among the three groups regarding maternal age ($P > 0.05$). However, regarding gestational age, the Schéffé test has revealed a significant difference between either patient group (SPE/HELLP or TTP/HUS) versus control group ($P < 0.05$ for each) (**Table 14**).

Assessment of Immature Platelet Fraction in Pregnancy-Associated Thrombotic Microangiopathy: (Results)

Table (14): Characteristics of patients with SPE/HELLP or TTP/HUS and normal controls

Variable	SPE/HELLP (n=24)	TTP/HUS (n=13)	Control (n=20)	F/ χ^2	DF	p-value
Age (years)	29.5 ± 5.6	25.3 ± 4.5	26.0 ± 4.6	4.086	2, 54	0.022¶†
Parity						
P0	6 (25.0%)	2 (15.4%)	5 (25.0%)	0.213	1	0.645§
P1	5 (20.8%)	7 (53.8%)	5 (25.0%)			
P2	8 (33.3%)	2 (15.4%)	6 (30.0%)			
P3	2 (8.3%)	1 (7.7%)	3 (15.0%)			
P4	2 (8.3%)	1 (7.7%)	1 (5.0%)			
P5	1 (4.2%)	0 (0.0%)	0 (0.0%)			
Previous abortions						
Nil	23 (95.8%)	12 (92.3%)	18 (90.0%)	1.319	1	0.251§
One	1 (4.2%)	1 (7.7%)	1 (5.0%)			
Three	0 (0.0%)	0 (0.0%)	1 (5.0%)			
Gestational age (weeks)	30.5 ± 4.0‡	29.8 ± 5.4‡	24.2 ± 3.2	14.597	2, 54	<0.001¶

Data are mean ± SD or number (%).

¶One-way analysis of variance (ANOVA).

§Chi-squared test for trend.

Assessment of Immature Platelet Fraction in Pregnancy-Associated Thrombotic Microangiopathy: (Results)

†No statistically significant difference among the three groups by the Schéffé post-hoc test.

‡P-value <0.05 versus Control group (Schéffé test).

Comparison between patients with SPE/HELLP or TTP/HUS and normal controls regarding to laboratory data:

1) Hemoglobin level: There was no significant difference between the three groups regarding hemoglobin ($P > 0.05$) (**Table 15**).

2) Hematocrit level: There was no significant difference between the three groups regarding hematocrit ($P > 0.05$) (**Table 15**).

3) Schistocytes count: There was high significant difference between the three groups regarding schistocytes count ($p < 0.001$). Applying Conover test reveal; significant difference between SPE/HELLP and control, between TTP/HUS and control and between SPE/HELLP and TTP/HUS (**Table 15**), (**Figure 18**).

Assessment of Immature Platelet Fraction in Pregnancy-Associated Thrombotic Microangiopathy: (Results)

Table (15): Hemoglobin level, hematocrit, and schistocytes count in patients with SPE/HELLP or TTP/HUS and normal controls

Variable	SPE/HELLP (n=24)	TTP/HUS (n=13)	Control (n=20)	F	DF	P-value
Hemoglobin (g/dl)	10.5 ± 1.6	11.1 ± 1.9	11.4 ± 1.2	1.773	2, 54	0.180¶
Hematocrit (%)	32.3 ± 5.7	33.1 ± 6.5	34.9 ± 3.3	1.457	2, 54	0.242¶
Schistocyte count (%)	0.5 (0.0 – 1.2)†	6.5 (0.8 – 17.6)†‡	0.01 (0.0 – 0.03)	27.186	2	<0.0001§

Data are mean ± SD or median (interquartile range).

¶One-way analysis of variance (ANOVA).

§Kruskal-Wallis test.

†P-value <0.05 versus Control group (Conover test).

‡P-value <0.05 versus SPE/HELLP group (Conover test).

Assessment of Immature Platelet Fraction in Pregnancy-Associated Thrombotic Microangiopathy: (Results)

[figure not shown]

Figure (18): Box plot showing the schistocyte count in patients with SPE/HELLP or TTP/HUS and normal controls.

